**Table 4-1 Excluded Diseases and Illnesses**

Body system or disease type	Known conditions excluded
Related to SBS	Ongoing radiation enteritis or the presence of damaged enteral tissue due to radiation enteritis  Active celiac disease  Refractory or tropical sprue  Pseudo-obstruction
Gastrointestinal	Active inflammatory bowel disease that requires chronic systemic immunosuppressant therapy that was introduced or changed during the last 3 months  Crohn's disease or other diseases that require biological therapy (eg, anti-tumor necrosis factor or natalizumab) that was introduced or changed in the last 6 months  Untreated known pre-malignant or malignant change in upper or lower GI biopsy or polypectomy  Known, untreated, polyposis conditions (ie, familial adenomatous polyposis, Peutz-Jeghers syndrome, Turcot syndrome, Juvenile polyposis syndrome, Cowden disease, Bannayan-Riley-Ruvalcaba syndrome, Gardner's syndrome, Cronkhite-Canada syndrome)  Intestinal or other major surgery scheduled within the time frame of the study  Chronic active pancreatitis or active cholecystitis
Immune	Compromised immune system (eg, acquired immune deficiency syndrome, severe combined immunodeficiency), hypersensitivity or allergies to teduglutide or its constituents or GLP-2
Psychiatric	Alcohol or drug addiction within the previous year  Major uncontrolled psychiatric illness

**Table 4-1 Excluded Diseases and Illnesses**

Body system or disease type	Known conditions excluded
General	Significant active, uncontrolled, untreated systemic diseases (eg, cardiovascular, respiratory, renal, infectious, endocrine, hepatic, or central nervous system)

#### **4.4 Subject Withdrawal Criteria**

All subjects are free to withdraw from participation in this study at any time, for any reason, specified or unspecified, without prejudice to further treatment. Discontinued subjects will not be replaced.

In all cases, the reason for withdrawal must be recorded in the case report form (CRF) and in the subject's medical records. If the reason is not disclosed, every effort must be made up to establish whether the reason was an AE and, if so, this must be reported in accordance with the procedures described in Section 6.2.1.2. As far as possible, all examinations scheduled for the early termination evaluations must be performed on all subjects who participate, but do not complete the study according to the protocol.

##### **4.4.1 Events Necessitating Withdrawal from Study**

The sponsor or designee should be consulted prior to premature withdrawal of a subject. The occurrence of any of the following events may necessitate premature withdrawal of a subject from the study:

- Development of any of the following Inclusion/Exclusion criteria that would interfere with analysis of the study results (ie, compromise PN/I.V.):
  - Significant active, uncontrolled diseases (eg, cardiovascular, renal, cancer) that would put the subject at any undue risk or prevent completion of the study
  - Major surgical interventions (eg, abdominal, vascular)
  - Crohn's disease flare up
  - Use of any excluded medication
  - Pregnant and lactating women
- Occurrence of a serious adverse event (SAE) thought to be related to study drug and not alleviated by symptomatic treatment
- Unwillingness to continue in the clinical study
- Death of the subject
- Investigator/Sponsor decision (ie, subject non-compliance with study procedures)

- Significant AE or medical decision that precludes the subject from adhering to study requirements

#### **4.4.2 Re-screening of Subjects**

In the event that a subject withdraws from the study in Stage 1, that subject may be re-screened upon the approval of the sponsor. A new subject number will be assigned.

Subjects whose urine output cannot be stabilized during the stabilization period after 1 repeated effort may not be rescreened.

### **5 TREATMENTS AND TREATMENT PLAN**

After signing the ICF, the subject will enter Stage 1 of the study, which includes screening, optimization and stabilization. The purpose of this stage is to ensure that all subjects are receiving and tolerating a stable minimal (optimized) level of PN/I.V. volume before treatment with teduglutide. If needed, the subject will enter an 8-week maximum optimization period, during which the PN/I.V. volume will be adjusted stepwise in targeted increments of 10% or more of the previous visit's volume ([Appendix 1](#)). Once the PN/I.V. volume is optimized, the subject will enter a minimum 4-week to 8-week stabilization period.

The aim of the study is to evaluate the efficacy of teduglutide in allowing reductions of PN/I.V. volume to less than the stabilized PN/I.V. level. After completion of the PN/I.V. stabilization period, subjects will enter Stage 2 of the study and receive teduglutide for a 24-week dosing period. The algorithm for the stepwise reduction of PN/I.V. during the Stage 2 dosing period is in [Appendix 2](#).

Stages 3 and 4 constitute the long-term extension portion of the study. Stage 3 will begin immediately following Stage 2 and Stage 4 immediately following Stage 3. In Stages 3 and 4, subjects can continue teduglutide treatment if deemed appropriate by the investigator. During the extension, the PN/I.V. dosage will be adjusted as described in [Appendix 3](#). Subjects will continue to receive teduglutide 0.05 mg/kg/day in Stage 3 for up to 24 months then in Stage 4 until teduglutide is commercially available for each subject, the subject's participation in this study is discontinued, or the study is discontinued.

Any subject who achieves complete independence from PN/I.V. support at any time during Stages 2, 3 or 4 will continue to receive teduglutide treatment. If a subject relapses following achievement of PN/I.V. independence, PN/I.V. support will be re-initiated and the subject will continue receiving teduglutide.

#### **5.1 Treatments Administered**

Teduglutide 0.05 mg/kg/day will be administered daily at home by the subjects, who will self-administer the study drug by SC injection into either thigh or arm or one of the 4 quadrants of the abdomen (in subjects without a stoma). For subjects with a stoma, the quadrant of the abdomen containing the stoma should not be used.

### **5.1.1 Identification of Investigational Product**

Teduglutide for SC injection is provided as a lyophilized powder that must be reconstituted using 0.5 mL sterile water for injection, and used within 5 minutes of reconstitution. The Injection Instruction Leaflets will be provided separately. Each 3.0 mL vial contains 5 mg of teduglutide.

Active ingredient:teduglutide

Added ingredients:L-histidine, mannitol, monobasic and dibasic sodium phosphate

Route of administration:SC injection

Dose:0.05 mg/kg/day

### **5.1.2 Packaging and Labeling**

Study drug will be packaged, labeled, and delivered to the clinical centers by the sponsor or designee. The study drug kit labeling will include the protocol number, the investigational drug warning, storage conditions, expiry date, drug name or drug code, lot number, sponsor name and country and In-Country Clinical Caretaker name and address. All medication supplied to be used in this study will be manufactured, tested, labeled, and released according to current legal requirements and Good Manufacturing Practice. Ancillary supply kits containing the following will also be provided with the study drug at each visit:

- Pre-filled syringes of sterile water for injection
- Needles to affix to sterile water for injection syringes for reconstitution; or vial adaptors for reconstitution and withdrawal of the reconstituted study drug into the dosing syringe
- Syringes and needles for injection (dosing)
- Alcohol swabs

### **5.1.3 Storage, Accountability, and Stability**

Study drug will not be dispatched to the center until the sponsor or designee has received all required documents from the study center in accordance with applicable regulatory requirements and relevant standard operating procedures.

The investigator or designee will conduct an inventory upon receipt of the clinical supplies and will acknowledge receipt of the supplies to the sponsor or designee. A copy of the shipping documents must be maintained for the investigator's records. Study drug must be kept in a locked area with access restricted to specific study personnel. Study drug must be stored refrigerated at a temperature between 2 and 8°C (36 to 46°F) until dispensed. Once dispensed to a subject, the study drug and the sterile water diluent should be kept at 15 to 25°C (59 to 77°F). If there are concerns that this temperature cannot be maintained, the study drug may be refrigerated. Therefore, the overall acceptable storage temperature range is 2 to 25°C (36 to 77°F).

Study drug kits will be dispensed to subjects at each of the study visits. Each study drug kit is sufficient for a treatment period of 1 week and enough kits are to be supplied to cover the period until the next planned study visit. The number of study kits dispensed at a study visit may be adjusted and study kits may be dispensed between study visits as an option at the discretion of the investigator and the subject. Additional study kits will be provided as necessary.

The investigator is to keep a current record of the inventory and dispensing of all clinical supplies. This record will be made available to the sponsor's monitor for the purpose of accounting for all clinical supplies. Any discrepancy or deficiency will be recorded, with an explanation. All supplies sent to the investigator must be accounted for and in no case will clinical supplies be used in any unauthorized situation.

All used and unused study drug vials, including the supplies must be returned by the subjects and retained at the center until instructions are received for return and/or destruction of supplies. Further details will be provided in the study reference manual.

## **5.2 Dose Regimen**

The volume of reconstituted study drug is to be administered at a fixed dose of 0.05 mg/kg. The dose will be calculated as an average of the 2 measurements of body weight at the stabilization and baseline visits. The dose of study drug administered at baseline should be maintained throughout the study period without adjustments for changes in a subject's weight except at Visit 26 when entering Stage 4 of the study.

### **5.2.1 Selection of Doses in Study**

The dose of teduglutide selected for this study is based on the efficacy and safety results of up to 2 ½ years of treatment in prior studies, as discussed in Section 1.3. Due to the favorable risk/benefit profile, the teduglutide dose of 0.05 mg/kg/day was chosen as the dose for all adult safety and efficacy studies.

### **5.2.2 Selection and Timing of Dose for Each Subject**

The study drug (teduglutide 0.05 mg/kg/day) will be self-administered immediately after reconstitution by SC injection into 1 of the 4 quadrants of the abdomen or into either thigh or arm. Subjects will be trained to self-inject teduglutide on Day 0. The first SC injection should be administered under the supervision of the investigator or designee and the subject observed for at least 4 hours. Detailed instructions for reconstitution and injection of the study drug can be found in the Injection Instruction Leaflets and the study reference manual. Each day, the injection site should be changed. Subjects with a stoma must avoid using the abdominal quadrant in which the stoma is situated.

The subject should be dosed at approximately the same time each day. If a subject forgets to take drug, that day's dose should be administered as soon as possible, even if this is later in the day or evening. Consecutive doses should be separated by approximately 12 hours.

First dosing with investigational product must be performed after the blood drawn for antibody testing at baseline (Visit 2) in Stage 2. Once the subject has started teduglutide treatment, dosing

must be performed at least 14 hours prior to the blood drawn for antibody testing, which will be performed at: Baseline and Weeks 12 and 24 during Stage 2; Months 6, 12, 18, and 24 (or early termination) during Stage 3; and every other visit (every 6 months) and end-of-study (or early termination) visit during Stage 4.

The investigator is responsible for contacting the sponsor or designee prior to interrupting or modifying the subject's daily study drug dosing regimen, ie, as consideration for tolerability issues.

A single discontinuation period of study drug should not exceed 10 consecutive days. Dosage interruptions of study drug are permissible for a maximum of 21 days total per each 24-week period throughout the study.

Dates of days with missed or incomplete doses are to be reported in the diary.

### **5.2.3 Subjects Who Achieve PN/I.V. Independence**

Any subject who achieves complete independence from PN/I.V. support at any time during the Stages 2, 3 or 4 treatment periods will continue to receive teduglutide treatment. A subject will be considered to have achieved independence from PN/I.V. (completely weaned off PN/I.V.) if the investigator prescribes no PN/I.V. and there is no use of PN/I.V. recorded in the subject diary at the last dosing visit.

If a subject relapses following achievement of PN/I.V. independence, PN/I.V. support will be re-initiated and the subject will continue receiving teduglutide.

### **5.2.4 Compliance with Dosing Regimens**

Subject compliance with study drug dosing will be monitored by the sponsor or designee by counting and examining used and unused vials. In addition, compliance will be checked at every visit by asking the subjects if they have taken their study drug according to instructions and by performing drug accountability.

Compliance is considered to be achieved if the subject has 80% of the planned doses administered.

### **5.3 Prior and Concomitant Medications**

The administration of all medications including concomitant medications (including prescription and nonprescription medications, dietary and nutritional supplements, and vitamins), study drug, and PN/I.V. must be recorded from screening and for the duration of the study in the appropriate sections of the CRF. Any diagnostic, surgical or other therapeutic treatments received by a subject during the course of the study will also be recorded on the CRF.

No new medications should be started unless medically necessary and prescribed by the investigator or by another qualified physician involved in the subject's clinical care and who is aware of the subject's study participation.

The mechanism of action of teduglutide may increase absorption of orally administered drugs (eg, motility medication, warfarin, psychotropics, and digoxin), so consideration should be given to modifying concomitant medication regimens. Down-titration of concomitant medication dosages should be considered when drugs, including those with a narrow therapeutic range, are given, especially if given at dosages that are higher than usual.

## 6 STUDY EVALUATIONS AND PROCEDURES

The objectives of this clinical study are to evaluate the safety, efficacy and pharmacokinetics of teduglutide in Japanese subjects with PN/I.V.-dependent SBS over a 24-week period (Stage 2) followed by a long-term extension (Stages 3 and 4) to evaluate safety and continued efficacy.

### 6.1 Efficacy Evaluations

Reductions in PN/I.V. volume form the basis for most of the efficacy evaluations. The procedures for the stepwise reduction of PN/I.V. during Stages 2 to 4 of this study are given in [Appendix 2](#) (Stage 2) and [Appendix 3](#) (Stages 3 and 4).

As described in Section [2.1](#), the efficacy endpoints for Stage 2 are as follows:

- Absolute and percent change from baseline in weekly PN/I.V. volume over 24 weeks
- Percentage of subjects who demonstrate a response at Week 20 and again at Week 24.
- Change in days per week of PN/I.V. support
- Changes in plasma citrulline levels from baseline to Week 24 (or EOT)

In Stages 3 and 4, absolute and percent change from baseline in weekly PN/I.V. volume and changes in days per week of PN/I.V. support and plasma citrulline levels will continue to be evaluated throughout the long-term extension (see Section [2.2](#)).

Single-dose pharmacokinetics will be evaluated on the first day of teduglutide treatment (Day 0) in Stage 2 only, and pharmacokinetic parameters will be derived as described in Section [2.3](#).

### 6.2 Safety Evaluations

Safety will be assessed by evaluations of the following variables:

- Adverse events, including GI symptoms
- 12-lead ECGs
- Vital signs, including changes in body weight and BMI
- Laboratory safety data, including electrolyte balance
- Antibodies to teduglutide and ECP (see [Table 6-1](#), [Table 6-2](#), [Table 6-3](#), and [Table 6-4](#) for timing)
- Changes in urine output (48-hour oral fluid intake/urine output)

- Abdominal ultrasound
- Upper GI contrast series with small bowel follow-through
- Colonoscopy/sigmoidoscopy of remnant colon
- Physical examinations

## 6.2.1 Adverse Events

During the study, the investigator is responsible for the detection and documentation of any AE or SAE, as defined in this protocol.

### 6.2.1.1 Adverse Event Definition

An AE is defined as any untoward medical occurrence in a subject or clinical investigation subject administered a pharmaceutical/medicinal product. An AE does not necessarily have to have a causal relationship with this treatment.

An AE can therefore be any unfavorable and unintended sign (including a clinically significant abnormal laboratory finding, for example), symptom, or disease temporally associated with the use of a medicinal product (investigational or marketed), whether or not considered related to treatment with the medicinal product.

An AE includes:

- An exacerbation of a pre-existing illness, sign, symptom, or clinically significant (as determined by the investigator) laboratory test abnormality and clinically significant ECG abnormality
- An illness, sign, symptom, or clinically significant laboratory abnormality that is detected or diagnosed after study drug administration
- Pretreatment or post-treatment events that occur as a result of protocol-mandated procedures

An AE does not include:

- The disease or disorder being studied or signs and symptoms associated with the disease or disorder, unless there is worsening of the condition of the disease or disorder
- A pre-existing disease or condition, present at the start of the study, that does not worsen

## Abuse, Misuse, Overdose, and Medication Error

Abuse, misuse, overdose, or medication error (as defined below) must be reported to the sponsor according to the SAE reporting procedure whether or not they result in an AE/SAE as described in Section 6.2.1.2. Note: The 24-hour reporting requirement for SAEs does not apply to reports of abuse, misuse, overdose, or medication errors unless these result in an SAE. The categories below are not mutually exclusive; the event can meet more than 1 category.

- **Abuse** – Persistent or sporadic intentional intake of investigational product when used for a non-medical purpose (eg, to alter one's state of consciousness or get high) in a manner that may be detrimental to the individual and/or society
- **Misuse** – Intentional use of investigational product other than as directed or indicated at any dose (Note: this includes a situation where the investigational product is not used as directed at the dose prescribed by the protocol)
- **Overdose** – An accidental or intentional administration of an excessive dose of a product
- **Medication Error** – An error made in prescribing, dispensing, administration, and/or use of an investigational product. For studies, medication errors are reportable to the sponsor only as defined below.

Cases of subjects missing doses of the investigational product are not considered reportable as medication errors.

Medication errors should be collected/reported for all products under investigation.

The administration and/or use of an expired investigational product should be considered as a reportable medication error.

### 6.2.1.2 Procedures for Reporting Adverse Events

Adverse events may be spontaneously reported by the subject, obtained through nonleading questioning, or noted during examination of a subject. Adverse events will be recorded from the signing of the ICF and for the duration of the study. Adverse events that are not resolved at the end of study will be monitored with a telephone call by the investigator, as necessary, for approximately 4 weeks after the last dose of study drug or until resolution or until the AE is judged by the investigator to have stabilized.

As they occur, new AEs will be recorded sequentially on the AE page of the CRF. The AE term should note the diagnosis whenever possible, not the individual signs or symptoms (eg, myocardial infarction should be recorded rather than chest pain, elevated cardiac enzymes, and abnormal ECG). Also recorded are:

- Start and stop date and time (date the site becomes aware of the SAE)
- Whether the event is continuing
- Frequency (intermittent, continuous)
- Intensity (mild, moderate, severe)

- Mild: usually transient, requiring no special treatment and generally not interfering with usual daily activities
- Moderate: usually ameliorated by simple therapeutic maneuvers and impairs usual activities
- Severe: requires vigorous therapeutic intervention and interrupts usual activities. Hospitalization may or may not be required
- Relationship to study drug (not related, related): identify relationship as “related” if a causal relationship between the investigational product and an AE is at least a reasonable possibility (see Section [6.2.2.2](#) for additional guidance on relationship to study drug)
- Whether the AE is serious (ie, an SAE). If identified as an SAE, the AE should be reported on the SAE form according to Section [6.2.2](#) below.
- Actions taken (none; study drug dose changed, interrupted, or discontinued; other medication change; nondrug therapy)
- Outcome (not recovered/not resolved, recovered/resolved, recovered/resolved with sequelae, recovering/resolving, unknown, fatal). An individual AE receives only one outcome.

Laboratory values, blood pressure, ECG evaluations, and clinical findings at the scheduled physical examinations must be reported as AEs if they:

- Are considered clinically significant by the investigator (ie, not part of the subject’s medical history),
- Fulfill SAE criteria, and/or
- Cause subject discontinuation from the study.

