## 6.2.2 Serious Adverse Events

An SAE must be recorded on the SAE Form. An SAE requires expeditious handling to comply with regulatory requirements. Any SAEs occurring from the signing of the ICF through 30 days after the last dose of study drug or the end of the study, whichever is longer, will be captured and must be reported within 24 hours after the investigator is made aware of the event.

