### **6.2.17.1 Colonoscopy/Sigmoidoscopy**

A colonoscopy/sigmoidoscopy of the remnant colon with polyp removal will be performed prior to teduglutide exposure (during stabilization) in subjects with any colon remnant including rectal stump evaluation. This will be repeated at Visit 10 in Stage 2, at Visit 25 (Month 24 or early termination) in Stage 3, and at end-of-study (or early termination) visit in Stage 4. A colonoscopy is required at the beginning of the study, at the end of the 24-week and 24-month treatment periods, and at the end of the study to determine if any clinically significant changes have occurred. The date and result of colonoscopy are to be recorded in the CRF. If a subject had a normal colonoscopy within 6 months prior to screening, a baseline colonoscopy/sigmoidoscopy will not be required.

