**Table 6-4 Schedule of Evaluations and Procedures – Stage 4 (Extension)**

Procedures	Every 3-Month Visit a	EOS (or early termination)
Visit Number:	V26, 27, 28, etc.	EOS
Visit Window (days)	± 7	± 7
Adverse events	X	X
Urine pregnancy test	X	X
Physical examination b	X	X
Vital signs	X	X
Body weight and BMI	X	X
Concomitant medications	X	X
Safety laboratory tests	X	X
12-lead ECG		X
Colonoscopy/sigmoidoscopy of remnant colon		X
Citrulline	X	X
Antibodies to teduglutide and E. coli protein c	(X)	X
Drug dispensing	X	
Interim safety visit	[X] d	[X] d
Diary e	X	X
48-hour oral fluid intake f (Diary)	X	X
48-hour urine output f (Diary)	X	X
Evaluation of PN/I.V. (actual volume L/week)	X	X
Teduglutide dosing	X g	
Compliance h	X	X

(X)=assessment to be performed only every other visit (every 6 months); [X]d=possible interim safety evaluation time point (Refer to footnote "d"); BMI=body mass index; ECG=electrocardiogram; EOS=end of study; L=liter; PN/I.V.=parenteral nutrition/intravenous fluids; V=visit

Note: Study visits will be scheduled every 3 months throughout the Stage 4 period. Interim (standard of care) visits may be utilized to assess subjects' well-being (ie, occurrence of adverse events) and to check for any changes in medications.

a Subjects will undergo a clinic visit every 3 months until teduglutide is commercially available for each subject, the subject's participation in this study is discontinued, or the study is discontinued.

b Full physical examination to be performed at end-of-study (or early termination) visit; a brief examination will be performed at all other study visits.

c Sample for antibody testing must be drawn at least 14 hours after dosing. To be collected at every other visit only (every 6 months) and end-of-study (or termination) visit.

d Interim safety evaluations will be performed 5 to 7 days after any scheduled visit when a reduction has been made to the subject's PN/I.V. volume. Hematocrit, serum blood urea nitrogen and serum creatinine, and urine sodium will be measured.

e The diary is to be completed for the 2-week period prior to every clinic or telephone visit.

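### Minor, cheap improvement: new non-serious adverse events are not sought after a subject's end-of-study or early termination visit, although a colonoscopy is mandated there and some subjects stop teduglutide outright

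*Protocol*

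**What the plan says.** All references are to the current, 4-stage version of the protocol.

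- **Recording of adverse events (6.2.1.2):** "Adverse events will be recorded from the signing of the ICF and for the duration of the study". The next sentence reads "Adverse events that are not resolved at the end of study will be monitored with a telephone call by the investigator, as necessary", for about 4 weeks after the last dose or until the event resolves or stabilizes.
- **Serious events (6.2.2):** captured "through 30 days after the last dose of study drug or the end of the study, whichever is longer".
- **Definition (6.2.1.1):** adverse events include "Pretreatment or post-treatment events that occur as a result of protocol-mandated procedures". Signs of the disease under study are excluded "unless there is worsening of the condition of the disease or disorder".
- **Colonoscopy (6.2.17.1):** in subjects with any remnant colon, repeated at Week 24, at Month 24 "and at end-of-study (or early termination) visit in Stage 4". Section 4.4 adds "As far as possible, all examinations scheduled for the early termination evaluations must be performed on all subjects who participate", including those who do not complete the study.
- **Schedule (Table 6-4):** the last column is the subject's EOS or early termination visit. The only later contact is conditional: "Interim safety evaluations will be performed 5 to 7 days after any scheduled visit when a reduction has been made".
- **Special interest (6.2.3):** polyp growth and neoplasia are notified within 24 hours whether serious or not.

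**The concern.** Two kinds of new, non-serious event can be foreseen just after the final visit, when nobody is scheduled to ask.

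1. **Procedure complications.** The last colonoscopy belongs to that visit. The definition treats its complications as adverse events, but the recording window closes as they would begin to appear. Colonoscopies at Week 24 and Month 24 in continuing subjects are not affected, because recording goes on.
2. **Loss of drug effect.** Under Section 3.2 a subject can leave because participation or the study is discontinued, and Section 6.2.4 requires withdrawal on pregnancy. Such a subject may stop teduglutide on a fluid prescription lowered during treatment, possibly to zero (Appendix 3, step 5b). Section 8.2.1 states that weaning is not expected in this population without increased absorption from teduglutide. New dehydration or worsening after stopping is therefore plausible.

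Non-serious does not mean trivial. Section 6.2.1.2 allows a severe event without hospitalization, and Section 6.2.2.1 does not make an emergency outpatient attendance without admission an SAE unless another criterion is met. Safety is a stated objective and minimum enrolment is 5 (Section 4.1), so one missed subject shifts an incidence by 1/5 = 20 percentage points.

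**Working it through.** The plan gives no figure to reproduce. The check compares the windows and then puts days on them.

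**Step 1: which end of study is meant?** Section 6.2.1.2 sets its telephone follow-up at about 4 weeks after the last dose, so it treats the end of study as a point close to that dose. Table 6-4 labels the subject's own last visit EOS. Both favour a subject-level reading, although the wording is not airtight.

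**Step 2: is anything scheduled afterwards?** The columns of Tables 6-2, 6-3 and 6-4 end at the last or early termination visit. The interim visit depends on a reduction in parenteral support. On the subject-level reading it falls after the window has closed, so it adds a contact but no recording days. Section 6.2.4 points to a follow-up period in Section 3.2, but Section 3.2 defines none.

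**Step 3: days covered.** Let d be the days from last dose to final visit, with d ≥ 0. The protocol does not give d, so the values below are assumed. On the subject-level reading:

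- new non-serious events, days after last dose: now d
- serious events, days after last dose: now max(30, d)
- both, after the fix: d + 30
- days after the final visit: non-serious now d − d = 0; serious now max(30, d) − d; both after the fix (d + 30) − d = 30

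| d (assumed) | Non-serious now, after last dose | Serious now, after last dose | Both after fix, after last dose | Serious now, after final visit |
|---|---|---|---|---|
| 1 | 1 | 30 | 31 | 29 |
| 14 | 14 | 30 | 44 | 16 |
| 30 | 30 | 30 | 60 | 0 |
| 60 | 60 | 60 | 90 | 0 |

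The 0 days for non-serious events after the final visit, and the 30 after the fix, hold for every d.

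**Step 4: why both sections must change.** If only 6.2.1.2 were extended, non-serious recording would outlast serious capture whenever d > 0: 44 against 30 days at d = 14, and 60 against 30 at d = 30.

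**Step 5: who is affected.** The colonoscopy part concerns subjects with remnant colon. The fluid part concerns those who stop outright. The document gives neither number.

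**The case against.** The strongest reply is that the study's duration may mean the whole trial. In Section 6.2.2 the alternative end date matters, on a subject-level reading, only when the final visit falls more than 30 days after the last dose, which makes a trial-level reading plausible there. Spontaneous reports are also accepted, and the definition shows an intention to capture post-treatment procedure events. This stands as a point about wording. It does not close the gap in practice: on the trial-level reading a departed subject stays under open-ended recording with no routine contact, so these events are still not sought.

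The second reply is that little is left uncaptured. That is largely right. Events evident at the final visit are covered by the adverse event row of Table 6-4. Serious events within the 6.2.2 window, special-interest events and events already open are handled. Subjects who go straight to commercial drug do not lose its effect. Mere return of underlying disease signs is not an adverse event under 6.2.1.1; only worsening is.

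A reader might infer something stronger: that the sections contradict each other, that serious complications generally go unreported, or that late drug toxicity is missed. The documents do not support this. A shorter window for non-serious events is a choice, serious events have their own tail, and with a half-life of about 2 hours (Section 1.1) late toxicity is not the issue.

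**Conclusion.** The point holds as a minor improvement to a window that is fixed badly. On the subject-level reading, new non-serious events are recorded for 0 days after the final visit, although a mandated procedure and, for some subjects, withdrawal of an active drug occur at or near that time. The conclusion rests on that reading of 6.2.1.2, on at least some subjects having remnant colon or stopping outright, and on assumed values of d for the days after last dose. The number of events missed cannot be estimated from the document. No efficacy endpoint is touched, and nothing here shows that the main safety conclusions would change.

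**What to change.** In both 6.2.1.2 and 6.2.2, set one common window for all adverse events, serious or not: from ICF signature through 30 days after the later of (a) the last dose of study drug and (b) the subject's final visit or final protocol-mandated procedure. If the sponsor means the whole trial in 6.2.2, state the common window as the minimum, so that SAE capture is not shortened.

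Add to Tables 6-2, 6-3 and 6-4 one closing telephone contact at the end of that window for subjects who stop teduglutide outright or who have an end-of-study or early termination colonoscopy. Ask about new events and record any commercial teduglutide use at onset, so that attribution stays clear.

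The cost is a signed protocol amendment, possibly with IRB and regulatory notification or approval (Section 9.5), and at most one call per subject by existing staff: 5 calls at the minimum enrolment of 5, or 10 if 10 were enrolled. Collection lasts somewhat longer and slightly more events will be reported.
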